**Table 6. Study CO-338-097 Schedule of Assessments**

Procedure	Screening Phase D-28 to D-1 b	Treatment Phase a (±3 days of scheduled timepoint)						Post-treatment Phase			
		Cycle 1			Cycle 2		Cycle 3+	EOT	FU-28 28 ±3 d after last oral/IV dose	FU-100 100 +7 d after last IV dose	LTFU
		D1 c,d	D15 e	D28	D1 d	D15 d	D1 d				
Informed Consent e	X										
Medical/Oncology History f	X										
Physical Examination g , Height g , Weight	X	X	X		X	X	X	X	X	X	
ECOG Performance Status	X h	X			X		X	X	X	X	
Vital Signs	X	X i	X i		X i	X i	X i	X	X	X	
Adverse Events j	X	X	X		X	X	X	X	X i	X i	X j
Prior/Concomitant Medications and Procedures	X	X	X		X	X	X	X	X	X	
12-lead ECG k (local lab)	X							X			
Hematology l (local lab)	X h	X	X		X	X	X	X	X	X m	
Clinical Chemistry n (local lab)	X h	X	X		X	X	X	X	X	X m	
Serum Pregnancy Test o (local lab)	X h	X			X		X	X			
Urinalysis p (local lab)	X h	X	X		X	X	X	X	X	X	

**Table 6. Study CO-338-097 Schedule of Assessments**

Procedure	Screening Phase	Treatment Phase a (±3 days of scheduled timepoint)						Post-treatment Phase			
		Cycle 1			Cycle 2		Cycle 3+	EOT	FU-28 28 ±3 d after last oral/IV dose	FU-100 100 +7 d after last IV dose	LTFU
	D-28 to D-1 b	D1 c,d	D15 e	D28	D1 d	D15 d	D1 d				
Disease Assessment/Tumor Scans q,r	X						X r (Start on C4D1)	(X) s	X t	X t	X t
Mandatory Tumor Tissue Biopsy/Resection/Sample	X u			X v				(X) w			
Peripheral Blood Samples for Biomarker Analyses x (central lab)	X	X			X		X	X	X	X	
Rucaparib Dispensation/Administration		X			X		X				
Nivolumab IV Administration y					X		X				
Plasma PK Sample z (central lab)		X aa			X aa		X aa		X aa	X aa	
Survival and Subsequent Treatments											X ab
CA-125 Measurement (local lab)	X	X			X		X	X	X	X	X

Abbreviations: AE(s) = adverse event(s); AESI(s) = adverse event(s) of special interest; ALP = alkaline phosphatase, ALT = alanine aminotransferase, ANC = absolute neutrophil count, AST = aspartate aminotransferase, BUN = blood urea nitrogen, CLCr = creatinine clearance; CO2 = carbon dioxide; CR = complete response, CT = computed tomography, ctDNA = circulating cell-free tumor DNA; D = day of cycle; ECG(s) = electrocardiogram(s), ECOG = Eastern Cooperative Oncology Group; EOT = End of Treatment Visit; FFPE = formalin-fixed, paraffin-embedded; FU-100 = 100-day Follow-up Visit after last dose of IV study drug; FU-28 = 28-day Follow-up Visit after last dose of study drug (oral or IV, whichever is later); fT3 = free triiodothyronine; fT4 = free thyroxine; FU = follow-up; HCO3 =

**Table 6. Study CO-338-097 Schedule of Assessments**

	Screening Phase	Treatment Phase a (±3 days of scheduled timepoint)						Post-treatment Phase			
		Cycle 1			Cycle 2		Cycle 3+	EOT	FU-28 28 ±3 d after last oral/IV dose	FU-100 100 +7 d after last IV dose	LTFU
Procedure	D-28 to D-1b	D1c,d	D15e	D28	D1d	D15d	D1d				

bicarbonate; HIV = human immunodeficiency virus; ICF = Informed Consent Form; LDH = lactate dehydrogenase, LTFU = long-term follow-up; MCH = mean corpuscular hemoglobin, MCHC = mean corpuscular hemoglobin concentration; MCV = mean corpuscular volume, MRI = magnetic resonance imaging, PET = positron emission tomography, PK = pharmacokinetic, PR = partial response or PR interval, QRS = QRS complex/interval; QT = QT interval; QTcF = corrected QT interval Fridericia's formula; RBC = red blood cell, RECIST = Response Evaluation Criteria in Solid Tumors; SAE(s) = serious adverse event(s); T3 = triiodothyronine; T4 = thyroxine; TSH = thyroid stimulating hormone; WBC = white blood cell.

- a = Treatment cycles are 28 days. Unless otherwise specified, all assessments are to be completed within ±3 days of scheduled time point.
- b = Exceptions to this screening window include the mandatory tumor tissue collection for Cohorts A1 and A2 as described under footnote 'u'.
- c = Any procedures required on Cycle 1 Day 1 may be omitted if completed ≤ 3 days prior to first dose of study drug.
- d = Patients are to refrain from taking their first dose of rucaparib at home on these days. Procedures are to be completed before any study drug is administered.
- e = Consent may be completed outside the 28-day screening window as consent does not expire. Reconsent is not required if outside the screening window. The screening period begins with the first study-specific procedure, performed outside standard of care, and only after consent for study participation has been provided.
- f = Patient's medical record must include prior treatments received, dates of administration, date of progression, and radiology report(s) to support assessment of disease progression. gBRCA test results, if known, will also be captured.
- g = A complete physical exam should be performed at Screening and End of Treatment Visits; a limited physical exam may be performed at all other visits. Height at screening only.
- h = To be performed ≤ 14 days prior to the first dose of rucaparib. Serum pregnancy test to be performed ≤ 3 days prior to the first dose of rucaparib, if applicable.
- i = Vital signs (blood pressure, pulse, and temperature) to be taken on clinic visit days, after the patient has been resting for at least 5 minutes.
- j = AEs (inclusive of SAEs and AESIs) occurring after first dose of rucaparib through 28 days after last dose of rucaparib will be recorded. In addition, SAEs occurring after signing of the ICF and that were related to a screening procedure will also be reported. Ongoing SAEs, AESIs, and treatment-related Grade 3/4 AEs will be followed to resolution or stabilization, death, or until lost to follow-up. Only related SAEs and AESIs (regardless of causality) will be reported after the 28-day Follow-up Visit.

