### 7.4.7.2 28-day Safety Follow-up (FU-28)

The procedures to be performed for all patients 28 ( $\pm 3$ ) days after the last dose of study drug (oral or IV, whichever is later) are listed below.

- Physical examination

- Weight
- Vital signs
- ECOG performance status ([Appendix 3](#))
- Disease assessment for patients who discontinued treatment for reason other than disease progression or death. Tumor scans should continue to be performed at 12-week intervals (up to 7 days prior permitted) for the first 3 years after initiation of oral/IV combination study treatment and every 24 weeks thereafter until radiologic disease progression by RECIST v1.1, as assessed by the investigator, is documented
- Blood sample for ctDNA analysis should be collected at the same time as radiological imaging
- CA-125 measurement (Local) should be performed at the same time as radiological imaging
- Hematology (Local)
- Clinical chemistry (Local) (fasting is not required)
- Urinalysis (Local)
- PK and immunogenicity sample collection (Central) - according to [Table 7](#)
- AE monitoring
- Concomitant medications and procedures

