#### 7.4.7.3 100-day Safety Follow-up (FU-100)

The procedures to be performed for all patients at least 100 days (+7 days) after the last dose of IV study drug are listed below. If a patient remains on oral study drug after discontinuation of IV study drug, the 100-day Safety Follow-up Visit can be performed at a cycle visit, provided it has been at least 100 days since the last IV dose.

- Physical examination
- Weight
- Vital signs
- ECOG performance status ([Appendix 3](#))
- Disease assessment for patients who discontinued treatment for reason other than disease progression or death. Tumor scans should continue to be performed at 12-week ( $\pm 7$  days) intervals for the first 18 months years after initiation of study treatment and every 24 weeks thereafter until radiologic disease progression by RECIST v1.1, as assessed by the investigator, is documented
- Blood sample for ctDNA analysis should be collected at the same time as radiological imaging (Central)
- CA-125 measurement (Local) should be performed at the same time as radiological imaging.

- Hematology (Local) (only required if toxicities are present)
- Clinical chemistry (Local) (fasting is not required) (only required if toxicities are present)
- Urinalysis (Local)
- PK and immunogenicity sample collection (Central) - according to [Table 7](#)
- AE monitoring
- Concomitant medications and procedures

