#### 7.5.4 Safety Evaluations

##### 7.5.4.1 Adverse Event Assessment

The investigator has the responsibility for assessing the safety of the patients and for compliance with the protocol to ensure study integrity. During the screening period, unless otherwise required by local regulations, SAEs which are related to protocol-mandated assessments will be reported. Once enrolled and study drug is administered, patients will be monitored for all AEs/SAEs/AESIs during study participation and until 28 days after the last dose of study drug and 100 days after the last dose of IV study drug, whichever occurs later. After the 28-day (oral and/or IV, whichever occurs later) or 100-day (IV) window, only study drug-related SAEs and all AESIs, irrespective of causality, need to be reported. Any ongoing SAEs, AESIs, or treatment-related Grade 3/4 AEs will be followed until resolution or stabilization or until loss to follow-up. AEs and laboratory abnormalities will be graded according to the NCI CTCAE grading system (v5.0) and recorded on the eCRF.

Complete details for monitoring AEs, including the definition of drug-related AEs, are provided in [Section 8](#).

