### 8.2 Definition of a Serious Adverse Event

An SAE is any untoward medical occurrence that occurs at any dose (or, occurs after informed consent is given and prior to dosing if the SAE is related to a study procedure) that:

- Results in death. Any event resulting in death during the reporting period (from date of first dose of study drug through 28 days after last dose of oral drug and 100 days after the last dose of IV study drug, whichever occurs later) must be treated as an SAE and reported as such. An event related to a study procedure that occurs after informed consent, but prior to dosing that results in death must also be reported as an SAE.
- Is life-threatening (patient is at immediate risk of death from the event as it occurred)
- Requires in-patient hospitalization (formal admission to a hospital for medical reasons) or prolongation of existing hospitalization
- Results in persistent or significant disability/ incapacity
- Results in a congenital anomaly or birth defect
- Important medical events that may not result in death, are not life-threatening, or do not require hospitalization may be considered SAEs when, based on appropriate medical judgment, they may jeopardize the patient and may require medical or surgical intervention to prevent one of the outcomes listed in this definition. Examples of such events include allergic bronchospasm requiring intensive treatment in an emergency room or at home or the development of drug dependency or drug abuse.

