## 8.8 Recording of Adverse Events, Serious Adverse Events, and Adverse Events of Special Interest

Events that occur after signing of informed consent but prior to initiation of study drug, unless due to a protocol-mandated procedure, will be recorded on the Medical History eCRF. Any AE that occurs after first dose of study drug through 28 days after receiving the last dose of oral study drug or 100 days after receiving the last dose of IV study drug, whichever occurs later, will be recorded on the AE eCRF. After the 28-day or 100-day reporting window after discontinuation of treatment, only SAEs assessed as related to study drug and all AESIs, irrespective of causality, need to be reported. Information on the follow-up of AEs, SAEs, and AESIs is provided in [Section 8.9](#).

In order to avoid vague, ambiguous, or colloquial expressions, the AE should be recorded in standard medical terminology rather than the patient's own words. Whenever possible, the investigator should combine signs and symptoms that constitute a single disease entity or syndrome into a final diagnosis, if appropriate. For example, fever, cough, and shortness of breath may be reported as pneumonia, if that is a reasonable diagnosis.

Each AE is to be evaluated for **causal relationship** to the investigational drug, severity, and, seriousness. The action taken, and the outcome must also be recorded.

SAEs and AESIs that occur during the study or within 28 days after receiving the last dose of oral study drug or 100 days after receiving the last dose of IV study drug, whichever is later, whether or not related to study drug, must be reported immediately (ie, **within 24 hours** of knowledge of the event or additional information for a previously reported event) to the sponsor/SAE designee. The contact information for reporting of SAEs/AESIs can be found on the SAE/ AESI Reporting Form.

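### Table 6 footnote j stops adverse-event recording 28 days after the last rucaparib dose, against the 100-day post-nivolumab window in Sections 7.5.4.1, 8.8 and 9.8.1

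*Combined protocol and SAP*

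**What the plan says.** Footnote j is attached to the Adverse Events row of the Schedule of Assessments (Table 6, Section 7.1). Its first sentence reads "AEs (inclusive of SAEs and AESIs) occurring after first dose of rucaparib through 28 days after last dose of rucaparib will be recorded". Its last sentence reads "Only related SAEs and AESIs (regardless of causality) will be reported after the 28-day Follow-up Visit". In between, it keeps follow-up of ongoing SAEs, AESIs and treatment-related Grade 3/4 events.

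The text sections set a longer window:

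- Section 7.5.4.1 monitors all AEs, SAEs and AESIs "until 28 days after the last dose of study drug and 100 days after the last dose of IV study drug, whichever occurs later".
- Section 8.2, for events resulting in death, runs "through 28 days after last dose of oral drug and 100 days after the last dose of IV study drug, whichever occurs later".
- Section 8.8, which governs the AE eCRF, takes the later of the same two limits, in a sentence that begins "Any AE that occurs after first dose of study drug through 28 days after receiving the last dose of oral study drug or 100 days"; here too the longer period is counted from the final infusion. It also says that SAEs and AESIs in that window, "whether or not related to study drug, must be reported immediately".
- Section 8.9 uses the same window for follow-up of AEs.
- Section 9.8.1 defines a TEAE by the same window and tabulates numbers and percentages of patients with TEAEs.

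Two visits matter. FU-28 is anchored to whichever drug stopped later; Section 7.4.7.2, which allows ±3 days, introduces its procedures with the words "days after the last dose of study drug (oral or IV, whichever is later) are listed below". FU-100 comes no sooner than 100 days (with a 7-day allowance) after the final infusion, and its procedure list in Section 7.4.7.3 includes AE monitoring. Table 6 also marks the AE row at FU-100.

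**The concern.** The analysis window and the schedule's recording rule disagree. Section 9.8.1 counts events up to 100 days after the last infusion, but the footnote beside the AE row ends routine recording at 28 days after the other drug. I found nothing in the protocol that gives the text precedence over the table.

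The footnote can also disagree with itself. Its first sentence is anchored to rucaparib alone. Its last is anchored to FU-28, which follows whichever drug stopped later. The two cut-offs separate when nivolumab outlasts rucaparib, and Section 5.5 allows this because each drug is assessed separately for discontinuation.

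The footnote leaves out new non-serious AEs and new SAEs judged unrelated. The exception for AESIs does not clearly cover late nivolumab toxicity: Section 8.3 refers to an AESI list for rucaparib, while immune-mediated events are described separately in Section 8.4 by reference to the nivolumab brochure. A new non-serious immune-mediated event could therefore fall outside the footnote.

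Safety and tolerability of the combination is a secondary objective for both cohorts. Section 9.1 allows no imputation of missing data, so an unrecorded event is simply absent. The bias in TEAE incidence would be downward, and it could differ across the approximately 15 sites according to which passage each one follows.

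**Working it through.** The plan gives no figure to reproduce here; the check is date arithmetic.

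**Set-up.** Let day 0 be the last nivolumab infusion and day k the last rucaparib dose. A negative k means rucaparib stopped first.

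- TEAE and eCRF window (Sections 8.8, 9.8.1): ends at max(k + 28, 100). Section 7.5.4.1 counts its 28 days from the last dose of either drug, but gives the same end because 0 + 28 is always earlier than 0 + 100.
- Footnote j, first sentence: ends at k + 28.
- Footnote j, last sentence: changes the rule at FU-28, nominally max(k, 0) + 28.

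**Shortfall.** On the first sentence it is max(0, 100 − (k + 28)) = max(0, 72 − k). On the last sentence it is max(0, 100 − (max(k, 0) + 28)).

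| k (days) | TEAE window ends | First sentence ends | Shortfall | Nominal FU-28 | Shortfall, last sentence |
|---|---|---|---|---|---|
| 72 | 100 | 100 | 0 | 100 | 0 |
| 56 | 100 | 84 | 16 | 84 | 16 |
| 28 | 100 | 56 | 44 | 56 | 44 |
| 27 | 100 | 55 | 45 | 55 | 45 |
| 0 | 100 | 28 | 72 | 28 | 72 |
| −28 | 100 | 0 | 100 | 28 | 72 |

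The k = 27 row is a patient infused on Day 1 of a 28-day cycle (Section 5.4.2) who takes rucaparib through Day 28 of that cycle (supply under Section 5.4.1 lasts to the next Day 1). The other values of k are illustrations, not document figures.

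**Self-disagreement.** The two sentences differ by max(k, 0) + 28 − (k + 28) = max(0, −k) days. That is nil when k ≥ 0 and 28 days when k = −28.

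**FU-28 timing.** With the ±3-day window and k ≤ 0, the last-sentence shortfall is 100 − 31 = 69 to 100 − 25 = 75 days. Section 3.1.4 also lets FU-28 be held on the discontinuation date if that is at least 28 days after the last dose, so it can fall later and the shortfall can be smaller than 69.

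**Scale per patient.** Section 9.2 plans 18 to 43 patients in Cohort A1 and about 10 in Cohort A2. One patient whose only occurrence of a given TEAE is missed changes its incidence by 1/43 = 2.3, 1/18 = 5.6 or 1/10 = 10 percentage points.

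**The case against.** The strongest reply is that the design is settled and one footnote was left unaligned. Section 8.8 states what goes on the AE eCRF, Section 7.5.4.1 repeats the window and points to Section 8 for detail, AE monitoring takes place at every cycle visit, and FU-100 has AE monitoring both in Table 6 and in its own procedure list. A site working from those would collect everything. The footnote also keeps the events of most concern: related SAEs, all AESIs, and follow-up of ongoing treatment-related Grade 3/4 events. The primary endpoint is untouched.

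Much of this stands. It is a drafting inconsistency, not a flawed design, and data are at risk only where a site follows the footnote. It does not remove the conflict: scheduling AE monitoring at FU-100 while a footnote on the same row restricts reporting after FU-28 is part of the contradiction.

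A second reply is that the first sentence says what will be recorded, not what will be excluded, so only the last sentence truly restricts. On that reading the 100-day shortfall for k = −28 does not arise. The last sentence still falls 72 days short whenever nivolumab stops with or after rucaparib.

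Third, the per-patient percentages are only 1/n and say nothing about how many events would be lost. That is correct; they show scale, not expected bias. Finally, Sections 8.2 and 8.9 concern deaths and follow-up, so the direct recording conflicts are with Sections 7.5.4.1 and 8.8 and the analysis conflict is with Section 9.8.1.

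**Conclusion.** The concern holds. Footnote j is inconsistent with the recording rules in Sections 7.5.4.1 and 8.8 and with the TEAE definition in Section 9.8.1. It is also inconsistent with itself when nivolumab outlasts rucaparib. The shortfall depends only on the two stop dates: 72 days for a common stop date, 45 for rucaparib through the end of the last shared cycle, and none once rucaparib continues 72 days or more beyond the last infusion. If rucaparib stops 28 days before the last infusion, it is 100 days on the first sentence and a nominal 72 on the last.

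The consequence is conditional. TEAE incidence is understated only where a site applies the footnote and a patient has a new non-serious AE or unrelated SAE in the gap. With no event rates given for this period, neither the number of such patients nor the size of any bias or site difference can be estimated. The point is worth correcting because the cohorts are small and safety is a secondary objective, but it does not threaten the primary analysis.

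**What to change.** Rewrite both affected sentences of footnote j to match Sections 7.5.4.1, 8.8 and 9.8.1. The first should record all AEs, SAEs and AESIs from the first dose of study drug through the later of 28 days after the last oral dose and 100 days after the last IV dose. The last should restrict reporting to related SAEs and all AESIs only after that point. Correcting the first sentence alone would leave the restriction at FU-28 in place.

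The cost is one footnote and a little more AE data entry. No visit or procedure is added, because FU-100 already exists with AE monitoring. The laboratory and vital-sign periods in Sections 9.8.2 and 9.8.3 are defined separately and are not affected by this change.

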**Table 6. Study CO-338-097 Schedule of Assessments**

	Screening Phase	Treatment Phase a (±3 days of scheduled timepoint)						Post-treatment Phase			
		Cycle 1			Cycle 2		Cycle 3+	EOT	FU-28 28 ±3 d after last oral/IV dose	FU-100 100 +7 d after last IV dose	LTFU
Procedure	D-28 to D-1b	D1c,d	D15e	D28	D1d	D15d	D1d				

k = Heart rate, PR, QRS, QT, QTcF and rhythm. Investigator to review results and assess as normal or abnormal (clinically significant or not clinically significant). ECGs to be repeated as clinically indicated.

l = Includes RBC count and parameters (hemoglobin, hematocrit, MCV, MCH, MCHC), reticulocyte count, WBC count, and differential (with ANC), and platelet count. Blood will be analyzed by a local laboratory and results must be reviewed by the investigator prior to dosing with rucaparib. Additional and more frequent tests may be performed at the investigator’s discretion.

m = Only required if toxicities are present.

n = Includes total protein, albumin, measured or calculated CLcr (for CLcr calculation, the Cockcroft Gault formula or institutional standard formula can be used), BUN or urea, total bilirubin, ALP, ALT, AST, LDH, glucose, sodium, potassium, magnesium, chloride, CO2/HCO3, calcium, phosphorus, TSH, fT3, fT4, TSH, with reflexive fT3 and fT4 if TSH is abnormal on treatment, and total cholesterol. Total cholesterol testing does not require fasting. If pancreatitis is suspected clinically, serum lipase and amylase should be analyzed. Blood will be analyzed by a local laboratory and results must be reviewed by the investigator prior to dosing with rucaparib. Tests for hepatitis C antibody and hepatitis B surface antigen are required at screening. Testing for HIV must also be performed at screening if mandated locally by a given site. Additional and more frequent tests may be performed at the investigator’s discretion.

o = Women of childbearing potential must have a negative serum pregnancy test result ≤ 3 days prior to the first dose of rucaparib. A serum pregnancy test must be performed ≤ 3 days prior to Day 1 of every cycle from Cycle 2 and beyond during the Treatment Phase. A serum pregnancy test must be performed at the End of Treatment Visit.

p = Includes dipstick for protein, glucose, blood, pH, and ketones. If dipstick findings abnormal, perform microscopic evaluation. To be conducted at screening only, but may be conducted at other times as clinically indicated.

q = Disease assessment to include clinical examination and appropriate imaging techniques, including CT scans of the chest, abdomen, and pelvis, with appropriate slice thickness per RECIST; other assessments (MRI, X-ray, PET, and ultrasound) may be performed if required. The same methods used to detect lesions at baseline are to be used to follow the same lesions throughout the clinical study. If a patient has known brain metastases, this disease should be evaluated at each required assessment. Copies of CT scans will be collected from all patients. Independent radiology review may be conducted on all or a subset of CT scans.

r = Tumor scans to be performed at the end of every 8 calendar weeks (±7 days) during the Treatment Phase, from the start of the oral/IV combination treatment on Cycle 2 Day 1. A confirmatory scan should be performed ≥ 4 weeks after an initial response of PR or CR is observed. Patients who have been on study at

